The neuropsychological assessment in the proposed study is a unique approach to further characterize domain-specific cognitive function as a predictor of the ability to use exercise-based behavioral therapy. The baseline neuropsychological battery will provide additional domain-specific measures of cognitive function (SRTT, executive function, word retrieval) that will be analyzed in the context of the ability to learn and implement the exercise-based behavioral strategy. These preliminary data will provide further evidence to support or refute the hypothesis that learning the PFME-based adaptive strategy is a procedural task and that implementation of the task uses implicit memory rather than explicit memory systems. Further, because several of the selected tests have neuroanatomical correlates, these data could support the design of future studies involving functional brain imaging to understand mechanisms of learning in the context of neurodegenerative disease, thus building on imaging studies in non-PD populations with OAB^{15,16}.

Measures: Participants in both groups will complete the SRTT (task of procedural learning) in addition to a neuropsychological battery that will include evaluations of executive function and explicit memory at baseline. These assessments mirror the evaluation included in the BETTUR2 study, which will ultimately increase the power of the evaluation to determine mediators impacting implementation of behavioral therapy for urinary symptoms in persons with PD.

Data Analysis: The analysis for Aim 2a will determine if baseline cognitive function scores mediate successful outcome in the behavioral therapy group. Based on previously published research and our pilot studies, successful implementation of behavioral therapy will be defined as achieving at least a 2-point reduction in the ICIQ-OAB symptom score^{24,61,64}. Cognitive function will be evaluated as a continuous and categorical measure (MoCA 18-24 vs 25-30).

To explore other potential characteristics of successful behavioral therapy implementation, we will examine baseline characteristics that differ between those in the behavioral therapy group who demonstrate at least a 2-point improvement (reduction) in ICIQ-OAB symptom score versus those who report less improvement. Baseline characteristics will include gender, age, PD severity as measured by the MDS-UPDRS motor part 3 score (mild vs. moderate), depression as well as the pre-specified measures of cognitive function (SRTT and Wisconsin Card Sort Test). Baseline characteristics will be compared using chi-square or t-tests as appropriate.

We will examine the correlation between cognitive function tests of procedural learning and executive function with change in ICIQ-OAB score after behavioral therapy. Performance on the SRTT will be assessed as the mean change in time (milliseconds) between random and sequential tasks. Performance on the Wisconsin Card Sort Test will be assessed using the perseverative errors score. We will correlate these measures with the change in ICIQ-OAB score between baseline and 12-weeks post-randomization.

Baseline characteristics which are significantly associated with successful implementation of behavioral therapy will be included as part of a multivariable logistic regression model including SRTT performance, Wisconsin Card Sort Test perseverative errors score in order to determine if these cognitive domains are important in the central nervous system control of OAB symptoms in response to behavioral therapy.

Aim 2b: Compared to exercise therapy, does anticholinergic drug treatment for urinary symptoms worsen executive function and PD motor symptom severity?

Rationale: The standard treatment recommendation for urinary symptoms in PD is anticholinergic drug therapy, despite the fact that, guidelines for OAB in older adults *without PD* recommend an initial trial of behavioral therapy, which is free of any drug side effects^{17,18}. Anticholinergic bladder relaxants block the action of acetylcholine by competitively binding the muscarinic receptors in the bladder, leading to bladder smooth muscle relaxation. Muscarinic receptors are also involved in cognitive functioning and the use of older antimuscarinic bladder relaxants has been associated with an increased risk of cognitive side effects such as delirium and confusion⁶⁵. Chronic use of anticholinergic medications is associated with accelerated cognitive decline in PD⁴⁸. Newer anticholinergic bladder relaxants, such as solifenacin, are designed to have less risk of cognitive side effects because they specifically antagonize bladder muscarinic receptor subtypes instead of those in the central nervous system⁶⁵. As shown earlier in the URGE PD data, solifenacin reduced urgency UI in persons with PD and symptoms of OAB in a RCT; however, no cognitive assessments were conducted thus precluding a careful assessment of the impact of this drug on potential cognitive side effects³⁴. The proposed neuropsychological battery will include domain-specific assessments that will provide a unique opportunity to assess if bladder selective anticholinergic drug therapy has any measurable effect on cognition in PD.

It is well established that anticholinergic drug therapy also reduces the motor symptoms of PD⁶⁶. Anticholinergic drugs are used alone and in combination as treatments for motor symptoms in PD, particularly tremor⁶⁶. However, there is increasing concern that the overall burden of anticholinergic therapy paradoxically can have significant negative impacts on motor symptoms, by increasing the risk of falls, fractures, and postural instability^{47,67}. Indeed, one study found that adding a central cholinesterase inhibitor decreased the risk of falls by 50% among persons with PD and a history of frequent falls⁶⁸. The addition of anticholinergic drug therapy for urinary symptoms leads to an overall increase in anticholinergic burden, particularly for conditions impacted by muscarinic receptors.

Regardless of whether behavioral therapy proves to be inferior or non-inferior to drug therapy, understanding the potential association of drug therapy with cognition or PD motor symptom severity are important factors for patients and providers to determine next steps for treatment⁶⁹.

Measures: Participants in both groups will complete a baseline and 12-week neuropsychological battery as previously described including the MoCA test, SRTT, CERAD Word List subtest, Nonverbal/Spatial Reminding Test, Wisconsin Card Sort Test, and the Subject Ordered Pointing task. We will use the Anticholinergic Risk Scale⁴⁷ to calculate an overall anticholinergic drug score for participants in both groups based on medications listed at the randomization visit as a potential effect modifier. The MDS-UPDRS will be repeated at the 12-week visit. Thus, the behavioral therapy group will serve as a control group to assess the potential impact of solifenacin drug therapy on domain-specific cognitive function and PD motor symptom severity.

Data Analysis: [The analysis for aim 2b will generate data informing how central cognitive control of sensory integration and motor function are involved in the response to drug therapy.] Baseline and 12-week post-randomization cognitive tests will be evaluated using paired t-tests to assess for change within the drug group and two-sample t-tests for differences across groups (the behavioral therapy group will serve as a control for this analysis). Because cognitive impairment in PD most often manifests as impaired executive function, we will focus on tests of this domain, such as the Wisconsin Card Sort Test or the Subject Ordered Pointing Task in our evaluation of impact on cognition. The clock-draw test, as a component of the MoCA, is another assessment of executive function that is often performed in clinical practice. If changes are noted on domain-specific assessments of the neuropsychological battery, we will also examine correlation with clock draw scores obtained through the MoCA test. The Anticholinergic Risk Scale will be assessed based upon medications at randomization. The Anticholinergic Risk Scale score will be included in a multivariable model including baseline characteristics associated with changes in cognitive function in bivariable analyses.

To assess the potential impact on motor symptoms, we will assess the change in the motor symptom subscale of the MDS-UPDRS (part 3 score). Similar to the cognitive testing, baseline and 12-week post-randomization assessments will be evaluated using paired t-tests to assess for change within the drug group and two-sample t-tests for difference across groups, with the behavioral therapy group serving as a control for this analysis. Previous research suggests an increase in the MDS-UPDRS part 3 score of 4.6 points is associated with clinically relevant decline in motor function⁷⁰.

Visit Schedule

Visit 1: Baseline (One phone/telehealth session and one in-person session)

Explanation of study procedures and consent to be a participant

Interview: Demographics, continence and medical history, MoCA, LSA, GDS

Physical: Height, weight, vital signs, cardiac, pulmonary, and abdominal exam, genital and rectal exam, basic neurologic exam, MDS-UPDRS, determination of post-void residual by bladder ultrasound

Laboratory Examination: Urinalysis and BMP and HgbA1c if indicated

Education: How to complete bladder diary, handout take-home questionnaires (ICIQ-OAB and OAB-QOL)

Visit 2 (Part 1) : Randomization

Interview: Collect and review 7-day bladder diary, ICIQ questionnaires

Physical: Vital signs; review laboratory results; determination of post-void residual by bladder ultrasound if not conducted at first visit;

Procedure: **Randomization (Behavioral Therapy or Drug Therapy)**

Behavioral Therapy	Drug Therapy

Visit 2 (Part 2): Behavioral Therapy Randomization
 
Procedure: Neuropsychological battery, SRTT, Pelvic floor muscle exercise training
 
Education: specific behavioral techniques for constipation, modification of fluid intake or timed voiding
	
Visit 2 (Part 2) : Drug Therapy Randomization
 
Procedure: Neuropsychological battery, SRTT
 
Education: Medication

Visit 3: Behavioral Therapy (2 weeks)
 
Interview: Review PFME record, address new problems, reinforce practice at home and verbal feedback regarding muscle control
 
Education: Urge suppression strategy, management of stress-related urine loss (if applicable)
	
Visit 3: Drug Therapy (2 weeks)
 
Interview: Medication Management, Medication Side Effects
 
Education: Medication & Bladder Diary & Forms (to return at Visit 5)


Visit 4: Behavioral Therapy (4 weeks)
 
Interview: Review PFME record, address new problems, offer additional manual training session if subject is not satisfied with treatment or has < 25% reduction in episodes of UI based on bladder diaries.
 
Education: Reinforce strategy and PFME
	
Visit 4: Drug Therapy (4 weeks)
 
Interview: Medication Management, Medication Side Effects
 
Education: Medication and Reminder to complete Bladder Diary

Visit 5: Behavioral Therapy (6 weeks)
 
Interview: Discuss new problems, Satisfaction & Benefit questionnaire
 
Education: Reinforce PFME and urge strategy, Bladder Diary & Forms (to return at Visit 7)
	
Visit 5: Drug Therapy (6 weeks)
 
Interview: Collect and review bladder Diary; Medication Management, Satisfaction & Benefit questionnaire
 
Education: Medication & Bladder Diary & Forms (to return at Visit 7)

Visit 6: Behavioral Therapy (8 weeks)
 
Interview: Review PFME record, address new problems, offer additional manual training session if subject is not satisfied with treatment or has < 25% reduction in episodes of UI based on bladder diaries.
 
Education: Reinforce strategy and reminder to complete diary and forms
	
Visit 6: Drug Therapy (8 weeks)
 
Interview: Medication Management & Medication Side Effects
 
Education: Medication and Reminder to complete Bladder Diary

Visit 7: Behavioral Therapy (12 weeks)
 
Interview: Collect and Review diary, collect follow-up questionnaires (ICIQ and satisfaction & benefit), administer LSA, constipation, self-efficacy and adherence questionnaires
 
Procedure: Repeat neuropsychological battery
	
Visit 7: Drug Therapy (12 weeks)
 
Interview: Collect and Review diary, collect follow-up questionnaires (ICIQ and satisfaction & benefit), administer LSA, self-efficacy, and constipation questionnaires
 
Procedure: Repeat neuropsychological battery

Human Subjects:**a. Risk to Subjects**

Human Subjects Involvement and Characteristics: Men and women with PD recruited from the Atlanta, Birmingham, Richmond, and Philadelphia VAMCs as well as in the surrounding community. We propose randomizing 90 participants to either exercise-based behavioral therapy or drug therapy with Solifenacain. In order to complete the study in 80 participants, we anticipated having to screen approximately 180 PD patients to identify those with clinically significant OAB symptoms, and enroll approximately 45 participants in each group. These estimates are based on our experiences in the BETTUR PD and BETTUR2 pilot studies. In the BETTUR PD study, 33 individuals were screened to enroll 20 participants. Of the 20 participants who were enrolled, 17 completed the study demonstrating a 15% drop out rate once enrolled. To date, in the BETTUR2 study, we have screened 107 individuals to randomize 51 participants and have had 6 participants drop out (11.7% rate).

During FY16, 541 unique Veterans with PD were served by the Atlanta VA and surrounding CBOCs. For the BETTUR PD pilot, 14 of the 32 screened subjects were recruited from the Atlanta VA after mailing letters to 360 Veterans identified with a diagnosis of PD in the Metro Atlanta area in FY08. Recruitment was extended to a university-based movement disorders clinic to achieve the intended sample size of 20 enrolled subjects. For the BETTUR2 study, of the 65 persons who have undergone screening procedures thus far, 25 were Veterans and 40 were recruited from university-based movement disorders clinics in Atlanta and Birmingham in order to maximize the team's ability to recruit the intended sample size. Thus, we propose to recruit both Veterans and non-Veterans for the proposed study from the outset. The university affiliates in Atlanta (Emory), Birmingham (University of Alabama at Birmingham), Richmond (Virginia Commonwealth University), Philadelphia (University of Pennsylvania) all have active movement disorders programs, which enhance the overall resources available to the study.

The sample size is informed by the ICIQ-OAB symptom score reduction observed in the BETTUR PD and BETTUR2 studies of behavioral therapy for urinary symptoms in PD. Based upon the bladder diary-derived UI frequency data (consistent measure used in both behavioral and drug trials), the effect of behavioral therapy and drug therapy to reduce UI frequency is similar^{24,34}. The ICIQ-OAB symptom score range is 0-16, with higher scores indicating worse symptoms. A score ≥ 7 would indicate clinically significant OAB symptoms (urgency, frequency, urgency UI, nocturia) occurring on average at least *sometimes*. In our previous studies, we have observed a 2-3 point reduction in the symptom score, which represents a 12%-19% reduction from baseline^{24,64}. The minimally clinically important difference for the ICIQ-OAB is defined as a statistically significant reduction in the symptom score that is accompanied by a reduction in bother and improvement in OAB-specific QOL. Because the observed reduction (12%-19%) represents a statistically and clinically meaningful difference, we propose a non-inferiority margin of 15%. Thus, we will randomize 90 participants in order to complete the interventions in 80 participants, which assumes 85% power and a non-inferiority margin on the OAB symptom score of 15% at 12-weeks post-randomization.

Sources of Materials: The patients involved in this study will be seen in the Atlanta and Birmingham VAMC/GRECC Continence Clinics and the Philadelphia and Richmond PADRECCs. No tissue, blood, or urine samples will be stored during the study period as part of the protocol. For purposes of this research, baseline and treatment data will be stripped of all patient identifiers and each participant will be given a unique identifier for the study. Patient records will be stored in a locked cabinet in a locked office and will be accessible only to the Principal Investigator, Interventionist, Research Coordinator, Patient Recruiter, Site PI's ([name], [name], and [name]) and co-investigators ([name], [name], [name], [name]). Computer-based records will be maintained through the Veteran's Administration Computerized Patient Record System (CPRS), a secure network with password protection.

Potential Risks: Behaviorally-based intervention and treatment for urinary symptoms is both low risk and side effect free. During the course of a study in which questionnaires are used and bladder diaries are a source of outcome measure, some participants may find questions uncomfortable or find documenting voiding habits burdensome. Rectal or vaginal manual biofeedback occurs during a physical exam. The participant is instructed to squeeze against the interventionist's finger to isolate their pelvic floor muscles through a contraction. Similar techniques have been utilized in previous studies of exercise-based behavioral training for

urge incontinence and have shown clinically significant improvement with minimal discomfort^{20,23}. The discontinuation rate for enrolled subjects was 15% or less.

Solifenacina has been FDA-approved for OAB symptoms since 2004⁷¹. The most common side effects include dry mouth and constipation⁷¹. In a small study of adverse events among older (> 65 yrs old) versus younger (≤ 65 yrs old) adults taking solifenacina or oxybutynin, solifenacina was associated with lower incidence of side effects than oxybutynin⁷². Older and younger adults taking solifenacina had similar rates of treatment-emergent dry mouth. Another study of solifenacina or oxybutynin versus placebo among older adults with mild cognitive impairment showed no impact of solifenacina at a dose of 5 mg daily (10mg daily was not tested) on tests of executive function, working memory or reaction time compared to placebo⁷³. In the Urge PD study, which evaluated solifenacina in persons with PD, 1/9 individuals reported constipation, 2/9 reported dry mouth and 1/9 experienced urinary retention³⁴.

b. Adequacy of Protection from Risks

Recruitment and Informed Consent: Subjects for the current study have been recruited through the Movement Disorders clinics at the Atlanta VAMC, Birmingham VAMC, Philadelphia, and Richmond VAMC, where each site has at least one board-certified movement disorders neurologist. For the BETTUR PD pilot, recruitment was extended to the Movement Disorders clinic at Emory University because of slow recruitment at the Atlanta VAMC. For the BETTUR2 study, although an additional recruitment site was added at the Birmingham VA, both sites requested permission to recruit non-Veterans through their university-affiliated movement disorders program in order to reach the target sample size.

Fliers are posted in the medical center as well as a PowerPoint slide ad that is broadcast throughout the medical center closed circuit television system. Per VA procedures and with permission from the primary neurologist, letters are sent to Veterans with a diagnosis of PD, who are identified in the corporate data warehouse and confirmed through chart review, to inform them about the study and offer contact information for study staff. Study teams have also partnered with the Michael J Fox Foundation Fox Trial Finder and local Parkinson Support Groups in order to let the local community know about the study. All patients will have the opportunity to give informed consent after discussion with the study PI or research assistant in a private examination room. As a three-site VA study, study procedures and the informed consent form will be approved by the Central VA Institutional Review Board and the VA Research and Development committee at each site. All subjects will be given a copy of the consent to keep for their records.

Protection Against Risk: For purposes of this research, baseline and treatment data will be stripped of all patient identifiers and each participant will be given a unique identifier for the study. Patient records will be stored in a locked cabinet in a locked office and will be accessible only to the Principal Investigator, Interventionist, Research Coordinator, Patient Recruiter, and Site PI's ([name], [name], and [name]) and co-investigators ([name], [name], [name], [name]). Computer-based records will be maintained through the Veteran's Administration Computerized Patient Record System (CPRS), a secure network with password protection.

- Only personnel who are qualified and IRB approved and trained for maintaining the privacy of each participant will be permitted to view records.
- Each participant will be assigned a unique study ID that will be used on all study documents.
- All identified patient data will be maintained on a secure VA research server at each site.
- A separate tracking database with patient identifiers that provide a link to the unique study IDs will be stored on a secure VA research server at each study site.
- Participant study documents which are identified by the participant's unique study ID, will be scanned on a VA device behind the VA firewall and uploaded to an Atlanta VA research server that is accessible to BOSS PD study personnel from each study site who are credentialed through the VA Research service at each site.
- Only deidentified data will be entered into the Redcap database by study personnel who are credentialed through the Atlanta VA Research service.

At all visits (in-clinic and telephone) after the baseline assessment, we will incorporate a standardized side effects checklist that has been used by the Continence research team for studies involving anticholinergic bladder relaxant therapy. The most common side effects reported by persons taking solifenacina are dry mouth and constipation. The risk of acute urinary retention will be reduced by excluding those with a baseline post-

void residual of ≥ 150 mL by bladder ultrasound. All adverse events and severe adverse events will be reported to the IRB, VA ORD, and the DSMB per VA policies.

References

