We propose a three-site, RCT conducted at the Atlanta (lead site), Birmingham and Richmond VA medical centers to establish non-inferiority of pelvic floor muscle exercise-based behavioral therapy compared to drug therapy for urinary symptoms in adults with PD. Groups will be stratified by OAB symptom severity, PD motor symptom severity, gender, and site. We will randomize 90 participants in order to complete the study in 80 participants, assuming 85% power and a non-inferiority margin for the OAB symptom score of 15% at 12-weeks. **The primary outcome measure will be urinary symptom severity as measured by the ICIQ-OAB symptom score^{32,33}** collected at 3 time points during the study: baseline, 6 weeks, and 12 weeks. PFME-based behavioral therapy will occur over 3 visits conducted during the first 6 weeks as was performed in the BETTER2 PD study. Participants in the drug therapy group will also have 3 visits during the first 6 weeks in order to individually titrate solifenacin drug therapy according to a validated symptom scale. Solifenacin has been selected because this bladder-selective anticholinergic drug (less risk of cognitive side effects) is the only drug with published evidence of potential efficacy in PD³⁴. At baseline, randomized participants will undergo a brief neuropsychological battery adapted from our current study to assess cognitive factors that may predict a preferred treatment strategy. At the 12-week assessment, the brief neuropsychological battery and MDS-UPDRS will be repeated in order to assess any change associated with treatment allocation. Follow-up visits will occur at weeks 4 and 8 to ascertain side effects and assess treatment adherence.

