allow for exploratory analyses beyond the planned tests of implicit memory and executive function to assess for correlation between baseline cognitive function and ability to implement the behavioral therapy intervention. For instance, if the implementation of the behavioral intervention correlates with tasks of motor procedural learning, we might not expect it to correlate with tasks of declarative memory, thus providing further evidence that the task is one of implicit memory. Further, several of the tests have been linked with specific neuroanatomical regions of the brain and could provide preliminary data to support future studies involving functional imaging. The neuropsychological assessment will be repeated at visit 7 (12 weeks) in order to determine any change from baseline.

While solifenacin is a bladder-selective anticholinergic drug with less risk of negative cognitive impact than other anticholinergic bladder relaxants, the 12-week re-assessment of cognitive function in this study is important to understand the potential drug impact on cognition in the PD population. Persons with PD are at increased risk of developing cognitive impairment and are more susceptible to anticholinergic side effects of these medications (such as delirium, constipation, and dry mouth^{29,46-48}). Each testing session will last approximately 75 minutes, with breaks included to reduce fatigue. The measures are described below:

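### The exploratory argument that behavioral therapy relies on implicit rather than explicit memory rests on one correlation being present and another absent, and no test compares the two

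*Combined protocol and SAP*

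**What the plan says.** - **Enrollment and Neuropsychological Assessment.** The battery is said to allow exploratory work beyond the planned tests. The example given is that, if the behavioral intervention tracks learning of motor procedures, "we might not expect it to correlate with tasks of declarative memory, thus providing further evidence that the task is one of implicit memory".
- **Aim 2a, Rationale.** The data are described as preliminary evidence for or against the hypothesis that carrying out the strategy "uses implicit memory rather than explicit memory systems". The same paragraph lists word retrieval among the measures to be analyzed and says the data could support later imaging studies.
- **Aim 2a, Data Analysis.** "We will examine the correlation between cognitive function tests of procedural learning and executive function with change in ICIQ-OAB score after behavioral therapy". The measures specified there are SRTT and Wisconsin Card Sort perseverative errors: "We will correlate these measures with the change in ICIQ-OAB score between baseline and 12-weeks post-randomization". The final model is a "multivariable logistic regression model including SRTT performance, Wisconsin Card Sort Test perseverative errors score", plus any baseline characteristics that were significantly associated with success. The section names no declarative-memory score, no comparison of correlations, no alpha and no power.
- **Battery.** It includes the CERAD word list and a spatial selective reminding test, given at baseline to both arms.
- **Size.** "We will randomize 90 participants in order to complete the study in 80 participants" (Research Design and Methods), and "enroll approximately 45 participants in each group" (Human Subjects).

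**The concern.** The hypothesis is comparative: one memory system rather than another. The only route to it that the plan describes is a correlation found for one system and not found for the other. A non-significant correlation does not show that the true correlation is zero, or that it is smaller than the significant one. In a sample of about 40, a real and equal declarative-memory correlation will often be missed. The explicit-memory tests are collected but appear in no stated Aim 2a correlation, model or contrast, so the specified analysis neither makes the comparison nor guards against the informal one. At stake is a mechanistic statement, exclusivity of implicit memory, that is meant to help shape later imaging work. The primary outcome is not affected.

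**Working it through.** The plan gives no power, alpha or error rate for Aim 2a, so there is no figure of its own to reproduce.

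**Inputs from the documents.** About 45 enrolled per arm and 80 completers in total, so 80 / 2 = 40 in the behavioral arm. The pilot dropout rates agree: 45 × (1 − 0.117) = 39.7 and 45 × (1 − 0.15) = 38.3.

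**Assumed, because not stated.** Two-sided 0.05 for each correlation; equal true correlation r of SRTT and of one declarative test with change in ICIQ-OAB; inter-test correlation 0 or 0.3; normal data.

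**Step 1, threshold.** r_crit = t / √(n − 2 + t²), with t(0.975, 38) = 2.024. This gives 2.024 / √(38 + 4.098) = 0.312.

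**Step 2, how often the pattern appears when both matter equally.** Simulation, 100,000 trials of n = 40 per setting:

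| True r (both tests) | SRTT significant | Pattern, inter-test 0 | Pattern, inter-test 0.3 |
|---|---|---|---|
| 0.1 | 9% | 8% | 8% |
| 0.2 | 24% | 18% | 15% |
| 0.3 | 48% | 26% | 21% |
| 0.4 | 74% | 20% | 17% |
| 0.5 | 92% | 7% | 7% |

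Hand check at inter-test correlation 0, where the frequency is close to p(1 − p) with p the power for one test: 0.24 × 0.76 = 0.18; 0.48 × 0.52 = 0.25; 0.74 × 0.26 = 0.19; 0.92 × 0.08 = 0.07.

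**Step 3, once SRTT has come out significant.** The plan's reasoning starts from that point. The share of such trials in which the declarative test is not significant is the pattern frequency divided by SRTT power:
- r = 0.2: 0.153 / 0.237 = 65% to 0.183 / 0.237 = 77%
- r = 0.3: 0.209 / 0.477 = 44% to 0.258 / 0.477 = 54%
- r = 0.4: 0.167 / 0.742 = 23% to 0.201 / 0.742 = 27%

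**Step 4, sensitivity.**
- Inter-test correlation 0.5: 13-17% for r = 0.2-0.4, and about 6-7% at r = 0.1 or 0.5.
- Neither test truly correlated (r = 0): about 2% in the expected direction.
- Two declarative tests, r = 0.2-0.4: 5-18% if both must be non-significant, 17-35% if one is enough. The plan does not say how they would be combined.
- n = 65, an assumed total if BETTUR2 participants were added: 18-25% for r = 0.2-0.3, about 7% at r = 0.4.

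**Step 5, direct test.** Williams' test for two dependent correlations r₁ (SRTT) and r₂ (declarative), with inter-test correlation c, on n − 3 degrees of freedom:

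t = (r₁ − r₂) √{ (n − 1)(1 + c) / [ 2D(n − 1)/(n − 3) + r̄²(1 − c)³ ] }

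where D = 1 − r₁² − r₂² − c² + 2r₁r₂c and r̄ = (r₁ + r₂)/2.

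With equal true correlations it wrongly favors SRTT in about 2.5% of trials in every setting above. Its power, for inter-test correlation 0 to 0.3, is about 27-36% for 0.3 versus 0 and 45-61% for 0.4 versus 0. In that last case the significant/non-significant pattern appears about 71% of the time.

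**The case against.** The strongest reply is that the plan promises little. The passage is introduced as an example of exploratory work, its verbs are tentative, and it states no p-value rule. The Aim 2a question concerns motor skill learning and executive function, and its specified analysis contains no declarative-memory correlation. This stands. A reader might infer that Aim 2a will formally conclude in favor of implicit memory from this pattern, but the documents do not support that. They propose it only as further, preliminary evidence. The label does not repair the logic, though: the Rationale still expects the data to bear for or against a comparative hypothesis.

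A reader might also infer that the plan could support the hypothesis by chance alone. That is wrong. When neither test correlates with outcome, the pattern appears in the expected direction only about 2% of the time, much like the direct test. In the 15-26% settings procedural learning really does matter; only the exclusion of explicit memory would be mistaken.

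It is also fair to say that the range depends on unstated inputs, that word retrieval is mentioned among the measures to be analyzed, and that BETTUR2 is cited as adding power. No pooled analysis is specified, however, and an assumed n of 65 leaves the frequency at 18-25% for r = 0.2-0.3.

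Finally, the direct test is not powerful at this size, and the logistic model is already large for about 40 people. Both points stand and shape the fix. Neither justifies inferring a difference that has not been tested.

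**Conclusion.** The point holds as a flaw in a proposed exploratory interpretation. It is not a defect in the primary analysis or in a prespecified Aim 2a test. As written, the plan would treat a correlation present for procedural learning and absent for declarative memory as evidence that the two differ, with no test of the difference.

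With 40 behavioral-arm completers, two-sided 0.05, equal true correlations of 0.2-0.4, inter-test correlation 0-0.3 and one declarative test, that pattern occurs in about 15-26% of trials. It drops to about 6-8% at r = 0.1 or 0.5, and spans about 5-35% at r = 0.2-0.4 according to how two declarative tests are combined. The sample size comes from the documents; every other input is an assumption, so the range illustrates the risk and is not a property of the plan. The logical gap does not depend on those inputs.

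**What to change.** - In Aim 2a, Data Analysis, prespecify one explicit-memory score, for example a CERAD word-list recall score, scored in the same direction as SRTT learning.
- In the behavioral arm, correlate that score and SRTT with change in ICIQ-OAB on the same participants. Test the difference between the two dependent correlations (Williams or Steiger). Use the continuous change score and do not add another term to the small logistic model.
- Report both correlations and their difference with 95% confidence intervals. Reserve any statement that implicit memory is used in preference to explicit memory for a contrast that supports it, and label the result hypothesis-generating.
- In Enrollment and Neuropsychological Assessment, replace the inference from an absent correlation with a reference to this contrast.
- If BETTUR2 data are to be pooled, say so and state how.

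**Cost.** Wording and one contrast on data already collected, with no new visits or participants. The downside is power: about 27-36% for 0.3 versus 0 and 45-61% for 0.4 versus 0, so a positive claim of exclusivity is harder to reach and an inconclusive interval is a likely result.
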